#### 6.5.2 Quality of Life

The EQ-5D-5L, EORTC QLQ-C30, Skindex-16, FNAE and the Hornheide questionnaire questionnaires will be used in this trial to assess quality of life whilst the patient is on treatment. These should be completed at baseline and then at the pre-cycle assessment visits for cycle 5, 9, 13, 17, 21, 25, 29, 33 and end of treatment visit.

Please refer to Appendix 6 for contingency measures during extenuating circumstances.

6.6	Visit schedule

Trial Evaluation	Baseline	cycle 1	cycle 1 cycle 2	cycle 3	cycle 4	cycles 5-34	End of treatment	Months following completion of treatment visit 					
								3	6	9	12	18	24
	Within 7 days of registration	Within 7 days pre treatment	Within 5 days pre treatment	Within 5 days pre treatment	Within 5 days pre treatment	Within 5 days pre treatment	Within 6 weeks of day 1 of last treatment cycle						
Physical exam¹	Х	Х	Х	Х	Х	Х	X	Х	Х	Х	Х		
ECOG	Х	Х	Х	Х	Х	Х	X	Х	Х	Х	Х		
Vital signs and observations	Х	Х	Х	Х	Х	Х	Х	Х	Х	Х	Х		
12 lead ECG	Х												
Medical & cancer history	Х												
Haematology & biochemistry  including serum pregnancy test if required and eGFR assessment.	Х	Х	Х	Х	Х	Х	Х	Х					
Thyroid function tests 	Х	Х	Х	Х	Х	X 	Х	Х					
Serology - Viral screen (HIV, Hep B and Hep C)	Х												
Concomitant medications	Х	Х	Х	Х	Х	Х	Х	Х					
Adverse Events 	Х	Х	Х	Х	Х	Х	Х	Х					
Photography and MRI/CT scan of area encompassing the primary lesion)	Xe				X 	X8	Χ 	X8	X8	X8	X8		
Administration of cemiplimab 		Х	Х	Х	Х	Х							 
Quality of life questionnaire - EQ- 5D-5L, EORTC QLQ-C30, Skindex-16, FNAE and the Hornheide questionnaire	Х					X 	Х						
Survival and anti-cancer therapy								Χ	Χ	Χ	Χ	Х	Χ

- 1. Full physical examination to be carried out at baseline. All subsequent visits a limited physical examination to be performed.
- 2. Full blood count; urea, sodium, potassium, total calcium, creatinine (U&Es), ALP, ALT, Albumin, Bilirubin (LTFs) and LDH.
- 3. Thyroid function tests (TSH, T4 and T3), cortisol and glucose (random).
- 4. Thyroid function tests to be performed at cycle 5 and then every other cycle whilst on treatment.
- 5. To be collected from day 1 of treatment until 95 days from day 1 of the final treatment cycle. Any AEs that are ongoing at this time point will be followed to resolution.
- 6. Within 6 weeks prior to commencing first cycle of cemiplimab
- 7. Photography and MRI/CT scan (if required) to be performed within 12 weeks of C1D1 treatment +/- 7 days but prior to cycle 5.
- 8. Photography and MRI/CT scan (if required) to be performed within 12 weeks of previous scan +/- 7 days.
- 9. Cemiplimab 350mg to be administered on day 1 (- 2 days + 4 days) of a 21-day cycle
- 10. EQ-5D-5L, EORTC QLQ-C30, Skindex-16, FNAE and the Hornheide questionnaire to be performed at baseline, pre cycle 5, 9, 13, 17, 21, 25, 29, 33 and end of treatment visits.

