# 6.2 **On-treatment** assessments (within 7 days prior to cycle 1 and then within 5 days prior to each subsequent cycle of treatment)

Patients will be seen and assessed prior to each cycle of treatment. Please refer to Appendix 6 for contingency measures during extenuating circumstances. Assessment should include:

- Limited symptom-directed physical examination including vital signs (weight, blood pressure, heart rate, oxygen saturation and temperature).
- ECOG performance status.
- Full blood count, U+Es (including urea, sodium, potassium, total calcium and creatinine), liver function tests (to include ALP, ALT, Albumin and Bilirubin) and LDH. Thyroid function tests (including TSH, T4 and if required T3), cortisol and glucose (random) to be performed at each pre-assessment up to and including cycle 5 then every other cycle.
- Serum pregnancy test if required

- Estimated GFR to be assessed according to local practice (preferred technique of eGFR using the CKD-EPI formula (see Appendix 3)).
- Toxicity assessment (CTCAE v5.0) from day 1 of treatment up to and including 95 days after the last trial treatment.
- Updated recording of concomitant medication use, with relevant dates.
- Photography of skin lesion(s), including those being followed as target lesions. To be performed 12 weeks (+/- 7 days) after cycle 1 day 1 and before cycle 5. Subsequent photography will be taken every 12 weeks (+/- 7 days) from the previous photography whilst patient is on treatment. NB Target lesions need to be measured in both the longest diameter and the perpendicular diameter.
- MRI/CT scan (with contrast) only if being used to follow target lesions. Use the same modality and scan the same areas as in the baseline scan. Scan 1 to be performed 12 weeks (+/- 7 days) after cycle 1 day 1 and before cycle 5. Subsequent scans will then be performed every 12 weeks (+/- 7 days) from the previous scan whilst patient is on treatment.
- Completion of Quality of life questionnaires EQ-5D-5L, EORTC QLQ-C30, Skindex-16, FNAE and the Hornheide questionnaire at pre cycle 5, 9, 13, 17, 21, 25, 29, 33, and end of treatment visits.

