#### 6.3 End of treatment visit

Patients should be seen 3-6 weeks from the first day of their final cycle of treatment. Assessments should include:

- Limited symptom-directed physical examination including vital signs (weight, blood pressure, heart rate, oxygen saturation and temperature).
- ECOG performance status.
- Full blood count, U+Es (including urea, sodium, potassium, total calcium and creatinine), liver function tests (to include ALP, ALT, Albumin and Bilirubin) and LDH, thyroid function tests (including TSH, T4 and if required T3), cortisol and glucose (random).
- Serum pregnancy test if required
- Estimated GFR to be assessed according to local practice (preferred technique of eGFR using the CKD-EPI formula (see Appendix 3)).
- Toxicity assessment (CTCAE v5.0) from day 1 of treatment up to and including 95 days after the last trial treatment. Any AEs ongoing after this time will be followed to resolution.
- Updated recording of concomitant medication use, with relevant dates.
- Completion of Quality of life questionnaire EQ-5D-5L, EORTC QLQ-C30, Skindex-16, FNAE and the Hornheide questionnaire.

If the patient remains progression-free then the photography and MRI/CT scans will continue 12 weeks (+/- 7 days) from the previous scan

- Photography of skin lesion(s), including those being followed as target lesions.
   NB Target lesions need to be measured in both the longest diameter and the perpendicular diameter
- MRI/CT scan ONLY if being used to follow target lesions. Use the same modality and scan the same areas as in the baseline scan.

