#### Please also refer to Appendix 5.

Management and safety of individual patients is under the clinical judgement of the investigator who may choose to withhold study treatment even if hold criteria are not formally met as per protocol.

All treatment delays will be reported in the eCRF. A treatment delay >4 days for cemiplimab should be justified. Treatment may be delayed no more than 12 weeks to allow recovery from acute toxicity. After cycle 5 patients may have up to 3 weeks break in their treatment for reasons other than toxicity at the discretion of the PI (maximum of two breaks in the course of a patient's treatment). The reason for the break needs to be provided. Please also see Appendix 6 for contingency measures during extenuating circumstances. In case of treatment delay of greater than 12 weeks, the patient should discontinue the study treatment, unless there is strong evidence for tumour response justifying continuation. The investigator must discuss the rationale with the Chief Investigator before a decision is taken.

Subjects may resume treatment with cemiplimab when drug-related AEs resolve to grade 1 or baseline value and steroid use is reduced to ≤ 10mg/day prednisolone or equivalent.

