#### Quality of Life data

EQ-5D-5L, EORTC QLQ-C30, Skindex-16, FNAE and the Hornheide questionnaire Data collection within 14 days prior to cycles 5, 9, 13,17, 21, 25, 29, 33 and within 6 weeks of final cycle of treatment in the study. Analysis will use EQ-5D-5L Index Scores, EQ-5D-5L VAS and EORTC QLQ-C30, Skindex-16, FNAE and the Hornheide questionnaire domain scores. Absolute means at each assessment point will be compared against baseline. Percentage of respondents experiencing change +/- 0.3 SD and +/- 0.5 SD will be used to assess those experiencing a degree of meaningful substantive change.

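### On-treatment quality of life forms follow cycle number with no rule for a held cycle, so they tend to be completed after toxicity has settled; the pre-cycle window is given as both 5 and 14 days

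*Protocol*

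**What the plan says.** Protocol section 6.5.2 schedules the questionnaires at baseline and by cycle number during treatment: "These should be completed at baseline and then at the pre-cycle assessment visits for cycle 5, 9, 13, 17, 21, 25, 29, 33". The sentence goes on to add the end of treatment visit. Section 6.2 and footnote 10 of the visit schedule (6.6) give the same list, and section 6.3 repeats the end of treatment form: "Completion of Quality of life questionnaire EQ-5D-5L, EORTC QLQ-C30, Skindex-16, FNAE and the Hornheide questionnaire".

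Two windows are given for the pre-cycle forms. Section 6.2, which lists QoL among its assessments, is headed "within 7 days prior to cycle 1 and then within 5 days prior to each subsequent cycle of treatment", and the schedule column for cycles 5-34 also says 5 days. Section 11.4 says "Data collection within 14 days prior to cycles 5, 9, 13,17, 21, 25, 29, 33".

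Section 7.5.2 holds the dose for most drug-related non-skin events of grade 2 or worse, fatigue excepted, and for more severe or persistent skin events. A toxicity delay may last up to 12 weeks. On restarting it says: "Subjects may resume treatment with cemiplimab when drug-related AEs resolve to grade 1 or baseline value". Steroids must also have been reduced. Grade 2 fatigue and endocrinopathies controlled on replacement may persist at re-dosing.

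Tumour photography and scans are timed differently. The first falls 12 weeks after cycle 1 day 1, and each later one 12 weeks after the previous one (6.2, 6.5.1).

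**The concern.** When a QoL cycle is held for toxicity, its form moves with the dose, and the dose waits for recovery. The timing of the measurement then depends on the state being measured. QoL is a named secondary endpoint (2.3), and good tolerability is part of the hypothesis (2.1). Section 11.4 compares the mean at each assessment point with baseline and counts patients who change by 0.3 or 0.5 SD. A single-arm trial has no control group in which the same shift would occur.

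The missing-data rule in section 11.5 need not catch this. Its not-missing-at-random sensitivity analysis is triggered when more than 10% of data is missing, and a form that has moved is late, not missing.

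Separately, with two windows a form can be valid under one section and invalid under another.

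**Working it through.** No sample size or power figure bears on this point. The check is schedule arithmetic.

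**Inputs.** 21-day cycles (7.1); QoL at cycles 5, 9, 13, 17, 21, 25, 29 and 33 (6.5.2); toxicity delay up to 12 weeks, or 84 days (7.5.2); windows of 5 days (6.2, 6.6) and 14 days (11.4); end of treatment visit 3-6 weeks after day 1 of the final cycle (6.3); treatment for at most 2 years (section 3).

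1. **Schedule without delay.** Day of cycle c = (c - 1) × 21 + 1. Cycle 5 is day 85, cycle 9 day 169, cycle 13 day 253, and cycle 33 day 673. Elapsed weeks are (c - 1) × 3 = 12, 24, 36, ..., 96. Forms are 4 × 21 = 84 days apart, so with no delay they coincide with the 12-weekly tumour assessments.

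2. **Schedule with one maximal hold.** The gap between two forms grows from 84 to 84 + 84 = 168 days. One patient's cycle 9 form may fall at week 24 and another's at week 36.

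3. **A form completed at the visit where the dose is deferred.** Suppose it is completed d days before the planned dose (d from 0 to 5) and the hold lasts h days. It then lies d + h days before the dose actually given. Counting back from that dose, it is always outside the 5-day window once h exceeds 5, and always outside the 14-day window once h exceeds 14. The in-window form is then the one near the resumed dose. Under the 14-day window it may still fall late in the hold, so the choice of window affects which state is recorded. The protocol does not say whether the window counts back from the planned or the actual dose.

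4. **The two windows.** 5/21 = 24% of a cycle; 14/21 = 67%. A form completed 10 days before dosing meets 11.4 and fails 6.2.

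5. **The end of treatment form.** It is due on about days 22-43 of the last cycle. A hold starting when the next dose is due (day 22) can run to day 22 + 84 = 106. For a patient who stops after a long hold, the visit window may close before the decision to stop. A patient who holds and then resumes has no end of treatment form at that time.

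6. **Late time points.** 2 × 365 - 673 = 57 days. If holds count towards the 2-year limit, more than about 57 days of cumulative delay removes the cycle 33 form. The latest means then come from patients with few delays.

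7. **Illustrative size (assumed inputs).** Rise in the mean = share of patients due a form who are on hold × their deficit. Low: 0.05 × 0.3 SD = 0.015 SD. High: 0.20 × 1.0 SD = 0.20 SD. This takes every such form to move to full recovery, so it is an upper figure for the assumed inputs.

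**The case against.** The strongest reply is that the protocol is silent about held cycles, which is different from prescribing a late form. A site may complete the form at the planned visit, find the toxicity there, and then defer the dose. Section 11.4 does not say that forms outside 14 days are discarded. This stands, and it is why the bias is a risk and not a certainty.

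A reader might infer that QoL is collected only before a dose. The documents do not support that: the sentence in 6.5.2 ends with "visits for cycle 5, 9, 13, 17, 21, 25, 29, 33 and end of treatment visit", no dose follows that last visit, and it reaches patients who stop for toxicity. A reader might also infer that a dose is given only when all drug-related events have gone. Grade 1 events generally, grade 2 fatigue and controlled endocrinopathies may still be present (7.5.2). Nor can one say that the worst periods are skipped by design. QoL is due at only 8 of the 33 pre-dose visits for cycles 2-34, so many episodes fall between 12-weekly forms under any timing rule.

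It is also fair that tolerability is assessed mainly through CTCAE grading, which runs from day 1 to 95 days after the last treatment, and that QoL drives no decision. On the windows, any form within 5 days also satisfies 14. The 5 working days in Appendix 6 concern posted forms under extenuating circumstances and are not a third routine window.

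What remains is the absence of any rule for a held QoL cycle, the link between on-treatment timing and recovery, and the two conflicting windows.

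**Conclusion.** The concern holds for the on-treatment forms. They follow cycle number, no rule covers a held cycle, and re-dosing after a toxicity hold mainly awaits recovery. On-treatment means may therefore look better than they were, and a single cycle label may cover patients up to 12 weeks apart.

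The documents give neither the share of patients on hold nor their QoL loss, so the size cannot be fixed. The 0.015-0.20 SD illustration rests wholly on the assumed 5-20% and 0.3-1.0 SD. It lies below the 0.3 SD threshold in 11.4, but that threshold applies to change in individual patients, so the two are not directly comparable.

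The 5-day and 14-day windows contradict each other as written and must be reconciled. The primary endpoint is unaffected. The change is worth making because it is cheap and removes a dependence on toxicity from a secondary endpoint.

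**What to change.** Collect the on-treatment questionnaires every 12 weeks with the tumour photography or scan assessment, whether or not a dose is given at that time. The nominal times are weeks 12, 24, 36 and so on, which equal pre-cycle 5, 9 and 13 when nothing is delayed. Keep the end of treatment form.

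Tie the form to that assessment and use the assessment's own window. A separate ±7 days around fixed weeks from cycle 1 day 1 could conflict with it, because only the first photograph is timed from cycle 1 day 1. Later ones are ±7 days from the one before, so permitted drift can reach ±14 days at the second and ±21 at the third. State the one window in 6.2, 6.5.2, the schedule with its footnote 10, and 11.4. Analyse by week since cycle 1 day 1.

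The calendar basis already exists for imaging, and Appendix 6 has imaging continue through breaks for extenuating circumstances.

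The cost is a wording amendment. Time points will no longer match cycle numbers, and a form may be needed during a hold when there is no pre-dose visit. With no delay, the number of forms is unchanged. No dosing, hold or restart rule changes.

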#### 7 TRIAL TREATMENT

#### 7.1 Investigational Medicinal Products

The regimen consists of cemiplimab, total fixed dose of 350mg, given on day 1 (- 2 days + 4 days) of each 21 day cycle as an intravenous infusion over 30 minutes. Cemiplimab (REGN2810) is a high affinity hinge-stabilized IgG4P human antibody to the PD-1 receptor (PDCD1, CD279) that blocks PD-1/PD-L1 mediated T cell inhibition. Binding of the PD-1 ligands PD-L1 and PD-L2, to the PD-1 receptor found on T cells inhibits T-cell proliferation and cytokine production. Upregulation of PD-1 ligands occurs in some tumours and signalling through this pathway can contribute to inhibition of active T-cell immune surveillance of tumours.

Treatment will continue until disease progression or unacceptable toxicity for a maximum of 2 years.

Cemiplimab will be supplied free of charge.

Study medication will be stored and dispensed by the investigator site's pharmacy department in accordance with Good Clinical Practice, Good Manufacturing Practice and pharmacy department SOPs.

Please see pharmacy manual and Investigator's Brochure (IB) for product information, handling and preparation instructions. Vials should be stored according to their labelling and kept in their kit until use.

#### 7.3 Concomitant Medications

Any treatment administered, other than anti-cancer therapy, from the time of informed consent until 90 days after the last study treatment will be considered concomitant treatment. This includes medications and other therapies for which administration started before the study and will continue during the study, as well as any therapies started in the follow-up period to treat a study drug related AE. All concomitant treatments must be recorded in the study eCRF with the generic name, dose, dose unit, frequency, indication, and start/stop date, as appropriate.

Patients should receive full supportive care during the study including transfusion of blood and blood products, treatment with antibiotics, analgesics, erythropoietin or bisphosphonates where appropriate.

#### 7.3.1 Permitted concomitant treatments

- Antiemetics
- Antiallergic measures
- Standard anti-diarrhoeal treatments
- Supportive treatment as medically indicated for the patient's well-being (including hyperalimentation and blood transfusion) may be prescribed at the investigator's discretion.
- Palliative radiotherapy (8Gy/single fraction, 20Gy/5#, 30Gy/10#), except to target lesions.
- Physiologic replacement doses of systemic corticosteroids are permitted, even if >10 mg/day prednisone equivalents. A brief course of corticosteroids for prophylaxis (e.g. contrast dye allergy) or for treatment of non-autoimmune

- conditions (e.g. delayed-type hypersensitivity reaction caused by contact allergen) is permitted.
- Any other medication which is considered necessary for the patient's welfare, and which is not expected to interfere with the evaluation of the assigned treatment may be given at the discretion of the investigator.

#### 7.3.2 Prohibited Medications

Patients must **not** receive:

- Any other non-licensed, investigational drug or approved anticancer treatment including immunotherapy, targeted-therapy or biological therapies until end of study treatment other than the treatment assigned at registration.
- Immunosuppressive doses of systemic corticosteroids (>10mg/day prednisolone or equivalent) such as hydrocortisone, prednisone, prednisolone (Solu-Medrol®) or dexamethasone (Decadron®) within 4 weeks prior to starting cemiplimab and whilst on trial except in the case of a life-threatening emergency or to treat a drug-related adverse event.
  - NOTE: Bisphosphonates and denosumab are not prohibited.
- Live vaccines for the duration of the study treatment and for up to 5 half-lives after the last dose of study drug.

#### 7.4 Post-Study treatment

On completion of the study treatment or on stopping study treatment, subsequent treatment is at the discretion of the individual investigator. The investigator will record further treatment for the disease on the appropriate eCRF, including name/type of treatment and start and end dates.

#### 7.5 Guidelines for the Management of Toxicity

Subjects will be monitored continuously for adverse events (AEs) whilst on the study from day 1 of treatment until 95 days after the last treatment date.

If possible, toxicities should be managed symptomatically. If toxicity occurs, the appropriate treatment will be used to improve signs and symptoms including antiemetics for nausea and vomiting, antidiarrhoeals for diarrhoea, and antipyretics, and/or antihistamines for drug fever.

See below for management of cemiplimab related toxicities.

AEs associated with cemiplimab may represent an immunologic aetiology. These immune-related AEs (irAEs) can differ from and be more severe than AEs caused by agents belonging to other therapeutic classes. Early recognition and management may mitigate severe toxicity. Most irAEs are reversible and can be managed by interrupting cemiplimab, administration of corticosteroids and /or other supportive care. The following are the most common identified immune-related AEs associated with cemiplimab. Evaluation criteria for the complete list of identified risks can be found in the Investigator Brochure:

- Pneumonitis
- Colitis

- Hepatitis
- Endocrinopathies
- Skin adverse reactions
- Nephritis
- Infusion related reactions including systemic hypersensitivity

#### 7.5.1 Cemiplimab dose reduction

No dose reduction will be permitted for cemiplimab.

# 7.5.2 Cemiplimab dose delay

Cemiplimab should be delayed for the following:

- Any grade 3 or grade 2 lasting longer than a week, skin drug related AE, or suspected Stevens-Johnson syndrome or toxic epidermal necrolysis
- Any grade 3 drug related laboratory abnormality including Hypothyroidism/Hyperthyroidism and Type 1 diabetes related hyperglycaemia; exception for leukopenia and lymphopenia, ALT and bilirubin.
  - ALT/bilirubin delay dosing for drug-related grade ≥2 toxicity
- Any grade ≥2 non-skin, drug related AE except fatigue.
- Any AE, laboratory abnormality or intercurrent illness which in the judgment of the investigator warrants delaying the dose of study medication.

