#### **Exceptions:**

- Subjects may resume treatment in the presence of grade 2 fatigue.
- Drug-related pulmonary toxicity, diarrhoea or colitis must have resolved to baseline levels before treatment is resumed.
- Drug-related endocrinopathies adequately controlled with only physiologic hormone replacement may resume treatment

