#### 7.5.4 Treatment Discontinuation

- Any grade 4 drug-related AE or laboratory abnormality.
  - Exceptions for immune related (irAEs); grade 3 or recurrent grade 2 pneumonitis, grade 3 hepatitis, nephritis, neurological toxicity, myocarditis or pericarditis, any recurrent grade 3 irAE.
- Any infusion reaction grade ≥3 during or directly after cemiplimab infusion.
- Any dosing interruption to cemiplimab lasting longer than 12 weeks
- Any AE, laboratory abnormality or intercurrent illness which in the judgment of the investigator presents a substantial risk to the subject with continuing drug dosing.
- Patients diagnosed with progressive disease, unless continuation of cemiplimab
  is deemed to be of clinical benefit e.g. it is within the first 12 weeks of treatment
  and thought to be pseudo-progression, in which case it should be discussed with
  the Chief Investigator or nominated representative (if treatment continues trial
  activity also needs to be performed as per the visit schedule).

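### Section 7.5.2's hold and restart rules do not match for grade 3 drug-related fatigue, and it is unclear whether its grade ≥2 hold reaches laboratory and endocrine abnormalities

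*Protocol*

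**What the plan says.** The list of reasons for delay in Protocol section 7.5.2 has four main bullets: skin events, laboratory abnormalities, other adverse events, and investigator judgement.

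- **Second bullet (laboratory):** "Any grade 3 drug related laboratory abnormality including Hypothyroidism/Hyperthyroidism and Type 1 diabetes related hyperglycaemia", followed by "exception for leukopenia and lymphopenia, ALT and bilirubin". A sub-bullet adds "ALT/bilirubin delay dosing for drug-related grade ≥2 toxicity".
- **Third bullet (other events):** "Any grade ≥2 non-skin, drug related AE except fatigue". Fatigue is the only exception, and no grade is attached to it.
- **Fourth bullet (judgement):** "Any AE, laboratory abnormality or intercurrent illness which in the judgment of the investigator warrants delaying the dose of study medication".

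The restart rule in the same section begins "Subjects may resume treatment with cemiplimab when drug-related AEs resolve to grade 1 or baseline value" and adds a steroid condition. Its list of exceptions includes "Subjects may resume treatment in the presence of grade 2 fatigue", a stricter rule for pulmonary toxicity, diarrhoea and colitis, and a more lenient one for endocrinopathies controlled by hormone replacement.

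Section 7.5.2 refers the reader to Appendix 5, whose endocrine table makes withholding at grades 2 to 4 depend on clinical need. Section 7.5.4 lists grade 4 drug-related events and laboratory abnormalities as grounds for discontinuation, with no exception for fatigue. It also lists "Any dosing interruption to cemiplimab lasting longer than 12 weeks".

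**The concern.** Section 7.5.1 permits no dose reduction, so holding, resuming and stopping are the only ways to manage dosing. In a multi-centre trial those rules should give one answer for one patient. Here two questions have no single answer.

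The first is whether a patient with grade 3 drug-related fatigue should be dosed. The hold list does not stop dosing, but the restart rule would not let dosing begin again.

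The second is whether a drug-related laboratory or thyroid abnormality below grade 3, or a grade 3 leukopenia or lymphopenia, calls for a hold. The second bullet says no. The third says yes if such findings count as adverse events.

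What is at stake is patient safety and consistent exposure across sites. In a single-arm trial no control group would show that sites had read the rules differently.

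**Working it through.** No figure in the plan bears on this point, so the check sets the rules side by side. All events below are drug-related, and bullet numbers refer to the hold list in section 7.5.2.

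| Event | Listed hold | Restart rule or other text | Result |
|---|---|---|---|
| Fatigue, grade 2 | None (excepted) | Restart allowed | Consistent |
| Fatigue, grade 3 | None (excepted) | Restart not allowed | Mismatch |
| Fatigue, grade 4 | None (excepted) | Section 7.5.4: discontinue | Settled by 7.5.4 |
| ALT or bilirubin, grade ≥2 | Hold under the sub-bullet; same threshold as bullet 3 | – | No conflict |
| Leukopenia or lymphopenia, grade 2–3 | Bullet 2: none. Bullet 3: hold, if counted as an AE | – | Ambiguous |
| Hypo- or hyperthyroidism, grade 2 | Bullet 2: none. Bullet 3: hold, if counted as an AE | Appendix 5: only if clinically needed | Three different answers |
| Hypo- or hyperthyroidism, grade 3 | Bullet 2: hold | Appendix 5: only if clinically needed | Listed hold against conditional hold |

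**Fatigue.** The restart rule speaks of drug-related events in general, not only the one that caused the hold. A patient held for something else who has grade 3 fatigue therefore cannot restart, while a patient with grade 3 fatigue alone meets no listed hold. Suppose instead that only the event causing the hold must recover. A site that holds for grade 3 fatigue by judgement still cannot restart until it falls to grade 2, while a site that relies on the listed exception never stops. The mismatch survives either reading.

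**Does bullet 3 reach laboratory findings?** The text points both ways.

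- *Against:* bullet 4 and section 7.5.4 each name adverse events and laboratory abnormalities as separate items.
- *For:* bullet 2 classes hypo- and hyperthyroidism as laboratory abnormalities, but section 7.5 lists endocrinopathies among the immune-related adverse events, and the restart exceptions treat them as exceptions to the adverse-event rule. The same condition carries both labels within section 7.5.
- *For:* the restart rule mentions only adverse events. If these exclude laboratory abnormalities, a patient held under bullet 2 has no stated recovery criterion.
- *For:* the definition in section 8.1.1 does not exclude laboratory findings, and section 8.1.2 lists certain ALT and bilirubin rises as medically important events.

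**Length of a hold.** Section 7.5.2 allows a toxicity delay of up to 12 weeks: 12 × 7 / 21 = 4 cycles. This is the scale for one affected patient, not an expected effect in the trial.

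**The case against.** The strongest reply is that the dosing rules keep the two terms apart. Bullet 2 deals with laboratory abnormalities, bullet 3 with adverse events, and bullet 4 and section 7.5.4 name both. Reading bullet 3 to cover laboratory values would empty bullet 2 of its grade 3 threshold and its exemptions, and a specific rule normally prevails over a general one. This largely stands. A reader might infer that bullet 3 cancels the laboratory exemptions; the documents do not support that, and for ALT and bilirubin there is no conflict on any reading. The reply does not settle the thyroid case, where section 7.5 uses both labels and Appendix 5 adds a third rule.

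On fatigue, the reply is that a hold rule and a restart rule may differ on purpose, as they do for pulmonary toxicity, diarrhoea and colitis, and that the investigator may hold at any time. Both statements are true, so this is a mismatch between rules and not an instruction that cannot be followed. But discretion only adds holds. Nothing in section 7.5.2 says that a listed hold may be waived or which listed rule takes precedence.

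Three further inferences are tempting and should not be drawn:

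- *Fatigue of every grade is exempt.* Section 7.5.4 covers grade 4.
- *Severe fatigue would be dosed without review.* Section 6.2 requires assessment before each cycle, including toxicity grading and performance status. Only a mandatory hold is missing.
- *A delay beyond 12 weeks always ends treatment.* Section 7.5.2 allows continuation where there is strong evidence of response, after discussion with the Chief Investigator.

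**Conclusion.** The point holds in limited form. Grade 3 drug-related fatigue is treated differently by the hold list and the restart rule. Whether bullet 3 covers laboratory and endocrine abnormalities is unsettled, most clearly for hypo- and hyperthyroidism, where two bullets and Appendix 5 differ. Leukopenia and lymphopenia are ambiguous only if laboratory findings count as adverse events.

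The size cannot be stated, because the documents give no frequency for these events. The toxicity summary in section 11.4 counts patients with grade 3 or 4 events and the number of SAEs, not holds or discontinuations, so any effect on that result is indirect. Sample size, the two-stage decision rule and the error rates are untouched. The case for acting rests on patient safety and on consistent dosing between sites.

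**What to change.** Reconcile the hold list, the restart rule and the restart exceptions in section 7.5.2 with the endocrine table in Appendix 5, so that each of these has one meaning:

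1. which grades of fatigue each of the hold and restart rules covers;
2. whether bullet 3 includes laboratory and endocrine abnormalities or leaves them to bullet 2;
3. which text governs where section 7.5.2 and Appendix 5 differ on thyroid disorders.

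The clinical lead decides the content. No clinical rule is proposed here, and nothing above implies which passage should give way. The cost is a wording change at the next amendment, with no effect on sample size or analysis.
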